4.1.1 Design Overview

We will use a three-arm, multi-site randomized controlled superiority trial with stratification by SES and parallel design (Aims 1 and 2). One thousand one hundred patients (half higher SES and half lower SES) will be recruited from four large cancer centers over a 18-month period. Randomization will be at the clinician level, nested within study sites, and will involve data analyst blinding. In preparation for the trial, we will conduct semi-structured interviews in Year 1 with women of lower SES who have completed treatment for early stage breast cancer to adapt the “What Matters Most to You” subscale of the Decision Quality Instrument (DQI) for women of lower SES. For Aim 3, we will use interviews, field-notes, and observations to explore strategies that promote the encounter decision aids’ sustained use and dissemination using a theoretical implementation model. See study Gantt Chart on page 46.

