4.1.3 Controlling for Contamination

Since the randomization occurs at the clinician level, we are confident that the risk of contamination will be minimal⁸⁸. However, to control for any potential contamination and assess the fidelity of delivering each intervention, we will audio-record a sample of clinical encounters. We will record consented patients. The digital recorder will be constantly present in the consulting room and a research assistant will be present to turn the recorder on when required. The research assistant will enter the room each time so the breast surgeon does not know when they are being recorded. The recording light on each recorder will be taped over so recording status can not be discerned. We will also ask all patients to indicate at T2 which intervention was used in the encounter, using images of each intervention, and will use both intention-to-treat and as-treated analyses. We will train all clinicians in delivering the intervention according to their allocated arm. Clinicians in usual care will not be trained in the use of the interventions. If there is residual contamination, the bias will be towards a null effect. We will therefore be confident that any significant findings are actual and arise as a result of the interventions. Since there are many more physicians than centers, we anticipate having greater power with physician level randomization than with site level randomization, even if the effect size we estimate is reduced by contamination.

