4.3 Participants

4.3.1 Randomized Controlled Superiority Trial (Aims 1 and 2)

We will include 600 women at least 18 years of age with a confirmed diagnosis of early stage breast cancer (I to IIIA) (see inclusion/exclusion criteria below). Approximately half will be on

Medicaid or Medicare without supplemental insurance, or uninsured (lower SES population) and about half will be women with private insurance or Medicare with supplemental insurance (higher SES population) (see 4.3.4 for stratification by SES).

Participants will be recruited across the four study sites over 18 months.

To facilitate recruitment and retention, participants will be compensated for their time with a \$15 gift card at T2, T3, T4, and T5.

Participant Inclusion Criteria

The study team at each study site will use the following inclusion criteria:

- Assigned female at birth;
- At least 18 years of age;
- Confirmed diagnosis (via biopsy) of early stage breast cancer (stages I-IIIA);
- Eligible for both breast-conserving surgery and mastectomy based on medical records and clinician's opinion before surgery;
- Spoken English, Spanish, or Mandarin Chinese.

Participant Exclusion Criteria

The following exclusion criteria will be used:

- Transgender men and women;
- Women who have undergone prophylactic mastectomy;
- Women with visual impairment (because of the visual nature of the Picture Option Grid);
- Women with a diagnosis of severe mental illness or severe dementia;
- Women with inflammatory breast carcinoma.

Women who are receiving neoadjuvant therapy will be invited to take part in the study in the first nine months of the trial in order to be able to complete all follow-up assessments before the end of the trial. Their T3 assessment will occur after the neoadjuvant therapy has been completed and post-surgery. This may occur up to 7 months after T0 (baseline).

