4.7.4 Consent and Baseline Assessment

To promote patient-centeredness and facilitate recruitment among women of lower SES, a research assistant and a patient who has had breast cancer and has completed all treatments (“patient associate”) will recruit and consent all eligible participants at each study site. Each patient associate will be recruited from breast cancer advocacy groups, existing patient networks, and contacts already established at each site. An effort will be made to recruit patient associates from lower socioeconomic backgrounds.

Consent procedures will vary slightly at each site based on the patient flow and individual needs of each clinic however at each site the research assistant will be the primary role responsible for obtaining consent. At each site, written consent will be obtained for participation in the trial.

At the Joanne Knight Breast Health Center, the patient associate and research assistant will send the information sheet and introduction letter to all potentially eligible patients and call them a few days before their scheduled appointment. They will go over the information sheet and offer to discuss the study in more detail with the patient over the phone. Each eligible patient will be told that she is potentially eligible for participation in the What Matters Most study but that eligibility will be confirmed by her surgeon during the appointment. Eligible patients will have an opportunity to ask any questions they may have and decline participation in the study at this stage. Once all questions have been answered, if patients choose to participate, they will give verbal consent to take part in the study, assuming their surgeon confirms eligibility during their upcoming clinic visit. Finally, the patient associate or research assistant will ask the patient a series of questions using standardized interviews to complete the baseline questionnaire. We have successfully used this approach with low SES groups before. An interpreter will also be involved when necessary.

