the study and notify study staff if the patient is interested in participation at which point the research staff will obtain written consent and administer the questionnaires from T0 and T2. The study staff will approach the patient and introduce the study if the surgeon doesn't mention the study to the patient after the consultation.

Additionally, at all four sites, we will recruit participants after their surgical consultation **if they explicitly request this when first approached about the trial**. For these patients, research staff will obtain written consent and administer the questionnaires from T0 and T2 after the patient has her surgical consultation.

See Appendix D for a sample information sheet and consent form.

At all study sites, the patient associate and/or research assistant will attend the clinic whenever eligible patients are scheduled to attend a surgical consultation. They will be notified that the eligible patient has arrived by the registration staff.

At the Joanne Knight Breast Health Center, surgeons will give a card with the study name and researchers' contact details to all patients whose eligibility has been confirmed. The patient associate and/or research assistant will approach all patients who leave the consultation room with a card. The patient associate and/or research assistant will then check eligibility with the patient, obtain the signed consent, and help the patient complete the first follow-up assessment (T2).

At D-H, if verbal consent and the baseline assessment were done over the phone, the patient associate and/or research assistant will obtain the written consent (either before or after the surgical consultation), and help the patient complete the first follow-up assessment (T2). If for any reason, the patient is deemed ineligible after their consultation with the surgeon, they will be unenrolled in the study.

At NYU School of Medicine and Montefiore Medical Center, the first follow-up assessment will also be completed immediately after the surgical consultation.

At all sites, the research assistant or patient associate will read the questions to patients who cannot read or write by using standardized interviewing procedures in a private room. We will document whether the questionnaires were read to the patient using a standardized interview and whether the assistance of an interpreter was needed.

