4.7.5 Randomization

Randomization will be at the clinician level, nested within study sites. We will use an R script written by the study statistician for randomization of the surgeons. The statistician will be blinded to surgeon identification. At each site, patients who have given informed consent and are seeing one of the participating clinicians will be allocated to the clinician's corresponding arm (Option Grid, Picture Option Grid, or usual care).

Approximately the same number of patients in each socioeconomic stratum will be allocated to each arm. We will monitor accrual within each arm for each socioeconomic stratum at each site to ensure that each arm has a similar number of patients in each socioeconomic stratum. The total number of patients recruited at each site will be allowed to vary.

In the intervention conditions, each participant whose eligibility has been confirmed by the surgeon during the consultation will be given a copy of the Option Grid or Picture Option Grid by their surgeon and will use it in the clinic visit.

In the usual care condition, the patients will receive care as usual and will be given a study card at the end of the consultation to signal to the research assistant or patient associate that the patient has been enrolled into the study.

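### Surgeons who know their arm decide on eligibility during the consultation, and women found ineligible afterwards at Dartmouth-Hitchcock are unenrolled, so the analysed sample can be selected after allocation

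*Combined protocol and SAP*

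**What the plan says.** **Allocation and masking.** Section 4.1.1 states: "Randomization will be at the clinician level, nested within study sites, and will involve data analyst blinding". Section 4.1.3 adds: "We will train all clinicians in delivering the intervention according to their allocated arm". The surgeon therefore knows the arm before any patient is recruited.

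**The criterion that needs judgement.** Section 4.3.1 requires a woman to be "Eligible for both breast-conserving surgery and mastectomy based on medical records and clinician's opinion before surgery". The time limit is surgery, not the consultation.

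**When eligibility is settled.** Section 4.7.5, with no site limit, says: "In the intervention conditions, each participant whose eligibility has been confirmed by the surgeon during the consultation will be given a copy" of the aid. In usual care a study card is given at the end of the consultation to signal enrolment. At St. Louis (section 4.7.4), women give verbal consent and complete the baseline questionnaire by telephone and are told that "eligibility will be confirmed by her surgeon during the appointment". Surgeons there give a card "to all patients whose eligibility has been confirmed", and staff approach the women who leave with one for written consent and T2. At Dartmouth-Hitchcock the usual route has record review and surgeon confirmation before the mailing, but section 4.7.4 then adds: "If for any reason, the patient is deemed ineligible after their consultation with the surgeon, they will be unenrolled in the study".

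**Analysis set.** Section 4.8.2 promises intention-to-treat and as-treated analyses. It gives no rule for women who are not carded or are unenrolled.

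**The concern.** In a trial that randomises clinicians, patients enter after the arm is known, so an arm-aware decision on who counts as eligible can undo the balance that randomisation gives. Here that decision falls within or after the visit in which the arm is delivered.

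The selection is plausibly related to the primary outcome. Section 3 of the decision quality worksheet (Appendix C) asks whether and how fully each operation was discussed and whether the woman was asked which she wanted. A woman whose surgeon concludes in the visit that only one operation suits her would plausibly score low on those items, and she is also the woman most likely to go uncarded or be unenrolled. The treatment discourse analysis in section 4.8.6 shows that the distinction matters: it drops single-option transcripts only when the reason was medical rather than the surgeon's preference. The unenrolment sentence draws no such line.

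An ITT analysis of the women who remain does not repair this, and recruiting more women does not shrink it.

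**Working it through.** **1. The passages side by side.**

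| Site | Consent and baseline | Surgeon's eligibility decision | If not eligible |
|---|---|---|---|
| St. Louis | Verbal consent and baseline before the visit, conditional on confirmation | In the visit | No card; not approached for written consent or T2 |
| Dartmouth-Hitchcock, usual route | Verbal consent and baseline before the visit | Before the mailing; can be reversed after the visit | Unenrolled |
| NYU, Montefiore | Written consent and baseline before the visit | In the visit, by the general text of 4.7.5 | No rule stated |

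Table 3 lists allocation, by way of the surgeon's confirmation, in the column before baseline. That conflicts with the St. Louis text in 4.7.4 and with 4.7.5.

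**2. The plan's own power figure (section 4.8.1).** Inputs: effect 9.34, SD 12, ICC 0.05, 16 physicians, 20% attrition, two-sided 0.05.
- N = 1,100: patients per physician m = 1,100 × 0.8 / 16 = 55. Design effect = 1 + 54 × 0.05 = 3.70. Patients per arm = 293.3. SE = 12 × √(2 × 3.70 / 293.3) = 1.906. Power = Φ(9.34 / 1.906 − 1.96) = 99.84%, which agrees with the stated figure of more than 99.8%.
- N = 600: m = 30, design effect 2.45, 160 per arm. SE = 12 × √(2 × 2.45 / 160) = 2.10 for arm against arm, and 12 × √(2.45 / 320 + 2.45 / 160) = 1.82 for both aids against usual care.

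**3. Shift in one arm's mean.** Let q be the excess share of women lost from one arm, and let the lost women score 12 points (1 SD) below that arm's full group. The mean of those who remain rises by 12q / (1 − q). Both q and the gap are assumptions; the documents give neither.

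| q | Shift | Share of 9.34 |
|---|---|---|
| 0.02 | 0.24 | 2.6% |
| 0.05 | 0.63 | 6.8% |
| 0.10 | 1.33 | 14.3% |

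If the 12-point gap is measured against retained women instead, the shift is 12q, that is 0.24, 0.60 and 1.20.

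**4. If confined to Dartmouth-Hitchcock.** The original targets in section 4.3.4 (317 at each of three sites, 150 at NYU) give a share of 317 / 1,101 = 0.288. Then q becomes 0.0144 or 0.0288, and the shift is 0.18 or 0.36 points (2% to 4% of 9.34). No site targets are given for N = 600.

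**5. False-positive rate at N = 600 with no true effect.** For a shift b in the contrast, the rate is 1 − Φ(1.96 − b / SE) + Φ(−1.96 − b / SE).

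| b | Arm against arm (SE 2.10) | Both aids against usual care (SE 1.82) |
|---|---|---|
| 0.24 | 0.052 | 0.052 |
| 0.60 | 0.059 | 0.063 |
| 1.20 | 0.088 | 0.101 |

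The last column assumes that the whole shift falls on one side of that contrast, for example in usual care.

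**The case against.** Several stronger readings are tempting, and the documents do not support them.

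- **That surgeons may drop any woman for any reason.** In the Dartmouth-Hitchcock sentence that phrase qualifies the finding of ineligibility, so ineligibility is still required. The sentence does not say who makes the finding.
- **That unenrolment applies everywhere.** It stands in the Dartmouth-Hitchcock paragraph only. The usual route there already includes record review and surgeon confirmation, so later removals should be few.
- **That use of the aid shapes the eligibility decision.** Section 4.7.5 puts confirmation before the aid is handed over. Removal after the aid has been used is explicit only at Dartmouth-Hitchcock.
- **That St. Louis removes enrolled women.** Verbal consent there is conditional and written consent follows the card, so this is a recruitment-bias question.

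There are also safeguards. Staff pre-screen using the appointment system and pathology reports (4.7.3), and St. Louis staff check eligibility again with the patient after the card (4.7.4). Accrual is monitored by arm and SES at each site (4.1.2, 4.7.5). Discontinuation is tracked in REDCap (Table 3), reasons for dropout are recorded and reported (4.8.7), and CONSORT reporting is promised (4.7.11).

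All of this stands, and it narrows the point. It does not close it. Accrual counts by arm do not show who was turned away, the screening log in 4.7.7 is broken down by SES only, and nothing says that an uncarded or unenrolled woman counts as a dropout. The statement in 4.1.3 that bias runs towards the null concerns contamination, not selection.

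**Conclusion.** The point holds in this form. Arm-aware surgeons confirm eligibility in the consultation, one criterion is partly their opinion, and the ITT set is not defined for women lost at that step. The result is a risk of recruitment bias at St. Louis and of post-allocation exclusion at Dartmouth-Hitchcock.

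The size is unknown. An excess loss of 5% to 10% in one arm with a 12-point gap shifts that arm's mean by about 0.6 to 1.3 points, or about 0.2 to 0.4 if confined to Dartmouth-Hitchcock's original share of recruitment. At 2% it is negligible. The direction is also open: losing low scorers from an aid arm inflates its effect, while losing them from usual care dilutes it. A reader might infer that the results will be biased by arm; the documents show only that the rules allow it. The change is worth making because it is cheap.

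**What to change.** 1. **Settle eligibility before the visit.** At every site, where the diagnosis is known beforehand, record eligibility by the record review and surgeon confirmation that Dartmouth-Hitchcock already uses. Reconcile 4.7.4 and 4.7.5 with Table 3.
2. **Define the ITT set.** Include every woman who was eligible on that record and consented, verbally or in writing, before the visit. Offer her T2, subject to written consent, whether or not she was carded. Replace the unenrolment rule with retention in ITT, plus a sensitivity analysis that excludes women found ineligible on facts that pre-date the visit. State separately how women whom 4.7.4 allows to be recruited after the consultation enter the analysis.
3. **Log the losses.** Record uncarded and later-ineligible women by arm, surgeon, SES and reason, and report them in the CONSORT flow.

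A masked check by the site research assistant is not realistic: each site has three to five surgeons with fixed arms, the assistant enters the consulting room to start the recorder (4.1.3), and the assistant or patient associate photographs the aid at T2 (4.5.2).

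**Cost.** Protocol wording, earlier surgeon confirmation at three sites and extra log columns. A few women without two surgical options stay in ITT and slightly dilute the effect. The surgeon who confirms eligibility beforehand still knows the arm, so some recruitment bias remains possible, but the decision no longer draws on the visit itself.

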4.7.5 Randomization

Randomization will be at the clinician level, nested within study sites. We will use an R script written by the study statistician for randomization of the surgeons. The statistician will be blinded to surgeon identification. At each site, patients who have given informed consent and are seeing one of the participating clinicians will be allocated to the clinician's corresponding arm (Option Grid, Picture Option Grid, or usual care).

Approximately the same number of patients in each socioeconomic stratum will be allocated to each arm. We will monitor accrual within each arm for each socioeconomic stratum at each site to ensure that each arm has a similar number of patients in each socioeconomic stratum. The total number of patients recruited at each site will be allowed to vary.

In the intervention conditions, each participant whose eligibility has been confirmed by the surgeon during the consultation will be given a copy of the Option Grid or Picture Option Grid by their surgeon and will use it in the clinic visit.

In the usual care condition, the patients will receive care as usual and will be given a study card at the end of the consultation to signal to the research assistant or patient associate that the patient has been enrolled into the study.

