4.5.2 Secondary Outcome Measures

Secondary outcome measures will include treatment choice, assessed at T3 using patients' medical records, treatment intention, the validated three-item **CollaboRATE** measure of shared decision-making (SDM)^{103,104}, Chew's validated one-item health literacy screening question¹⁰⁵, PROMIS, an eight-item validated short form measure of anxiety¹⁰⁶, EQ-5D-5L, the validated, standardized six-item quality of life measure¹⁰⁷, the five-item validated decision regret scale¹⁰⁸, and four items from COST, a validated financial toxicity measure^{109,110}. We will also ask participants to estimate the out-of-pocket (OOP) portion of their medical expenses

over the past month. We will use the recordings of clinical encounters to analyze the extent to which SDM occurs using the five-item validated observer-rated OPTION⁵ scale¹⁰². We will also include a fidelity-of-use checklist derived from Wyatt's work to assess the actual use of encounter decision aids⁵⁶. Finally, we will use IntegRATE, a four-item generic patient-reported measure of integration of healthcare delivery^{111,112}. At T2 and T3, we will also investigate each intervention's patterns of use. At T2, the research assistant or patient associate will take a picture of each intervention post-consultation to determine how the intervention has been used and whether the patient/family and/or clinician have annotated it. At T3, participants will be asked to indicate how many times they used the intervention post-surgical consultation and whether family members, relatives, or caregivers have used the intervention.

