4.7.6 Follow-up Assessments

During the clinic visit, we will audio-record clinical encounters with consented patients to assess the fidelity of intervention delivery (T1). After the visit, participants will be asked to complete a second questionnaire (T2). Two additional follow-up assessments will occur around 1-2 weeks (T3) and 12 weeks post- surgery (T4) (Fig. 5). For participants recruited in the first nine months of the trial, we will also conduct a follow-up assessment 1 year post-surgery (T5).

Follow up questionnaires will be administered in the clinic, when possible, and aligned with regularly scheduled return clinic visits. If this is not possible, follow-ups will be conducted either over the phone, online (sent as an email via REDCap), or on paper (sent via mail with a pre-stamped, self-addressed envelope).

To minimize respondent burden and disruption and to accommodate varying levels of literacy and health literacy, validated short-form questionnaires will be used. Each follow-up assessment (T2, T3, T4, and T5) comprises 10-34 items.

We expect that T0 (baseline assessment) will take between 15 and 30 minutes. All subsequent assessments will take approximately 10 minutes.

For each assessment, the outcome measures will be combined into one questionnaire to improve ease of use (see Table 4).

Table 4. Number of items according to data collection point

Measure	Number of Items	T0 Baseline	T2 Post-Visit	T3 1 Week Post-Surgery*	T4 12 Week Post-Surgery**	T5 1 Year Post-Surgery
Health literacy	1	X				
Demographic survey	6	X				
Decision quality	16		X	X		
Knowledge (5-item subscale of DQI)	5	X	(X)	(X)		

Treatment intention (self-reported)	1		(X)			
Quality of life	6	X			X	
Anxiety	8	X	X	X	X	
Shared decision-making (self-reported)	3		X			
Decision regret	5			X	X	X
Integration of healthcare delivery	4	X			X	
Financial toxicity	5			X	X	X
Total number of items		30	27	34	28	10

* or first post-operative visit

** or second post-operative visit

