4.8.2 Analysis Plan

All data will be entered into REDCap, a secure research electronic data capture database (developed for the trial), and subsequently transferred to Stata for analysis. Initial examination of data will include descriptive statistics, frequency distributions, and histograms in order to identify outliers and missing data. All participants will be asked to indicate at T2 which

intervention they have received by being shown an image of each. Using this information, we will perform both an intention-to-treat and as-treated analysis.

4.8.3 Analysis Corresponding to Aim 1

Adapting the Decision Quality Instrument in Year 01.

We will use a two-step thematic analysis derived from descriptive phenomenology, assisted by the computer software ATLAS-ti. First, the transcripts will be coded to identify DQI items and instructions that require adaptation. In a second and more detailed analysis, the interview transcripts will be coded according to all the themes discussed in the interviews, including spontaneously emerging themes. Similar codes will be merged and subsequently grouped into families of codes and networks. Dual independent coding will be used for 100% of all interview transcripts, to ensure reliability of coding and to agree the themes and family of codes for all remaining interview transcripts. Discrepancies among raters will be discussed until agreement is reached.

Aim 1: Assess the comparative effectiveness of two effective encounter decision aids (Option Grid and Picture Option Grid) against usual care, on shared decision-making, decision quality, treatment choice and other direct outcomes in women, and differentially by SES.

We will first perform separate analyses for each follow-up period using linear and logistic regression models as appropriate for continuous (decision quality, SDM, quality of life, anxiety, decision regret, and IntegRATE) and binary (treatment choice) outcomes, respectively. The results will provide potentially valuable insights into how rapidly each intervention affects outcomes. Outcomes measured multiple times after T0 (anxiety, regret, decision quality, and financial toxicity) may also be analyzed using a longitudinal model. If the interventions are found to have an effect, a secondary analysis that adds predictors for the number of prior Option Grid and Picture Option Grid patients seen by the healthcare professional will examine whether there are physician learning effects under either intervention.

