- Other surgery: _____
- I am not sure

Section 2: Facts About Breast Cancer Surgery

We would like to check if we have done a good job at giving you information about breast cancer. Please answer the following questions using what you have read and heard from your care team so far.

2.1. For most women with early breast cancer, how much would waiting a few weeks to make a treatment decision affect their chances of survival?

- A lot
- Some
- A little or not at all.

2.2. With treatment, about how many women diagnosed with early breast cancer will eventually die of breast cancer?

- Most will die of breast cancer
- About half will die of breast cancer
- Most will die of something else

2.3. After which treatment is it more likely that women will need to have another operation to remove more tumor cells?

- Lumpectomy
- Mastectomy
- Equally likely for both

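### No rule stops women in the aid arms from consulting their copy of the aid while they answer the DQI knowledge items at T2

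*Combined protocol and SAP*

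**What the plan says.** - **Possession.** Section 4.7.5 says that a confirmed participant in either aid arm "will be given a copy of the Option Grid or Picture Option Grid by their surgeon and will use it in the clinic visit". Women in usual care receive care as usual and a study card.
- **Presence at T2.** Section 4.5.2 says that at T2 "the research assistant or patient associate will take a picture of each intervention post-consultation to determine how the intervention has been used". Section 4.5 places T2 immediately after the visit. For NYU and Montefiore, section 4.7.4 repeats that "the first follow-up assessment will also be completed immediately after the surgical consultation"; at the other two sites staff help the woman complete T2 after the consultation.
- **The test.** Section 4.5.1 and Tables 3 and 4 put the 16-item DQI, with its five knowledge items, at T2 and T3. The Appendix C instruction for those items reads "Please answer the following questions using what you have read and heard from your care team so far".
- **The image question.** Section 4.8.2 has all participants report at T2 which "intervention they have received by being shown an image of each". Its place relative to the knowledge items is not given.
- **T3.** Section 4.5.2 says that at T3 "participants will be asked to indicate how many times they used the intervention post-surgical consultation". Section 4.7.6 prefers completion in clinic; failing that, "follow-ups will be conducted either over the phone, online (sent as an email via REDCap), or on paper".
- **Direction of bias.** Section 4.1.3 argues that residual contamination would pull towards no effect, so that significant findings can be trusted.

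**The concern.** A knowledge test is meant to show what a woman has understood and retained. If a woman in an aid arm can glance at a sheet that carries some of the answers, a higher score may reflect access to the sheet. The plan has no safeguard against this and collects nothing that would separate look-up from learning afterwards.

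Knowledge is one of the three DQI scores, an Aim 2 disparity outcome and the first-named mediator in Aim 2, hypothesis 2. Look-up would favour the aids, so the reassurance in section 4.1.3 does not cover it.

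**Working it through.** **Step 1. Compare the knowledge items with the aids (Appendices A, B and C).**

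| Item | Topic | What the aids print |
|---|---|---|
| 2.1 | Effect of waiting a few weeks | Not covered |
| 2.2 | How many women eventually die of the disease | Not covered |
| 2.3 | Which surgery more often needs another operation to remove tumour | 20 in 100 for lumpectomy. No rate for mastectomy, where the text says possibly with positive nodes and yes with reconstruction |
| 2.4 | Which women live longer | Both aids state that survival is the same |
| 2.5 | Which women have more recurrence in the treated breast | Both aids give 5-10% within 10 years for either surgery; the Picture Option Grid adds that type of surgery is not what matters |

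Item 2.4 can be read off directly. Item 2.3 can be inferred, but the mastectomy column could mislead. Item 2.5 has a matching row, but the documents contain no answer key, so it is left out of the arithmetic.

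**Step 2. Look for a rule that closes the book.** Sections 4.5.2, 4.7.4, 4.7.5, 4.7.6 and 4.8.2 and the Appendix C instruction contain none. Table 4 lists 27 items at T2, which is 16 (DQI) + 8 (anxiety) + 3 (CollaboRATE). The image question is therefore outside that count, and its position is open.

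**Step 3. Possible size.** The assumptions, none of them in the documents, are: five items scored right or wrong on 0-100, hence 20 points each; a share w of 40-50% who would otherwise be wrong; a share f of 25-50% of those who look the answer up; every look-up correct; and no look-up in usual care.

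Shift = number of readable items × 20 × w × f

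- Item 2.4 only: 1 × 20 × 0.40 × 0.25 = 2 points, up to 1 × 20 × 0.50 × 0.50 = 5 points.
- Items 2.3 and 2.4: 2 × 20 × 0.40 × 0.25 = 4 points, up to 2 × 20 × 0.50 × 0.50 = 10 points.

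**Step 4. The plan's precision, for scale only.** Section 4.8.1 gives SD 12, ICC 0.05, 16 physicians, 20% attrition and a difference of 9.34.

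- At 1,100 women: 1,100 × 0.8 / 3 = 293.3 per arm and 1,100 × 0.8 / 16 = 55 per physician. The design effect is 1 + 54 × 0.05 = 3.70 and SE = 12 × √(2 × 3.70 / 293.3) = 1.91. Power is Φ(9.34/1.91 − 1.96) = 99.8%, which agrees with the plan. (The plan's stated design effect of 4.04 corresponds to 10% attrition; nothing here depends on that.)
- At 600 women: 160 per arm and 30 per physician. The design effect is 1 + 29 × 0.05 = 2.45 and SE = 12 × √(2 × 2.45 / 160) = 2.10.

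If that SD and ICC applied to the knowledge score, which the plan does not say, a 2-point shift with no learning would reach two-sided significance about 16% of the time: Φ(2/2.10 − 1.96) = 0.157, plus 0.002 from the other tail. A 4-point shift would do so about 48% of the time: Φ(4/2.10 − 1.96) = 0.48.

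**The case against.** A reader might infer that women sit the test with the aid in hand and that much of any knowledge gain would be copied from it. The documents do not say so. They place the aid in the visit and in front of a camera afterwards; they do not place it in use during the questionnaire. T2 is attended by staff, is read aloud to women who cannot read or write, and should take about 10 minutes. The Appendix C instruction covers what was read and heard, applies to every arm, and is not permission to consult a sheet.

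Nor is it established that two arms take an open-book test and the third a closed-book one. Section 4.4.3 gives usual-care women the site's ordinary information resources, which may be on paper and cover the same facts. The image question, if it cued usual-care women at all, would shrink the difference. A distortion of the Picture versus Option Grid contrast is conceivable, but both aids share the medium and the evidence, and no direction can be given.

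It is also tempting to divide the shift by 9.34. Section 4.8.1 gives that figure for the DQI without saying which of its three scores it describes, so such a percentage has no firm base.

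At T3 the objection is strongest. T3 follows surgery, up to 7 months after baseline with neoadjuvant therapy, so possession is likely but not assured. Rereading at home can fairly be seen as part of how the aid works. That is no reason to demote T3.

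All of this limits the size and certainty of the problem. It does not supply the missing rule at T2.

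**Conclusion.** The gap is real but narrow. At T2 the aid is present, the knowledge items follow directly after the visit, at least one of the five is answered on both sheets, and nothing prevents look-up. Any resulting bias favours the aids and affects the knowledge score only, not concordance or decision process.

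Its size is unknown. The 2 to 5 points (item 2.4 alone) and 4 to 10 points (items 2.3 and 2.4) rest entirely on the assumed scoring, error rates and look-up rates, and usual-care leaflets would reduce them. The point justifies a procedural change because the remedy is cheap and the bias cannot be separated from learning afterwards. It does not show that a knowledge effect in this trial would be spurious.

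**What to change.** - **T2, sections 4.7.4 and 4.7.6.** Women in all three arms put every paper from the visit away before starting T2. Women who consent after the consultation, and so complete T0 and T2 together, do this before T0.
- **Order at T2.** The DQI is completed first. Only then is the aid photographed and the image-identification question asked.
- **T3.** Add one yes/no item on whether any material was consulted while answering, and use it in a sensitivity analysis of T3 knowledge. Keep T3 as a planned DQI time point. Because consulting material is behaviour after randomization, that analysis should support the main one and not replace it.

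The cost is a sentence of site procedure, a fixed question order and one extra T3 item, with no added staff or visits. The downside is that the measured knowledge effect may be smaller than if the sheet were left out.
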